Spontaneous (non-traumatic) intracerebral haemorrhage (sICH) constitutes about 28% of all strokes worldwide (1). The prognosis is poor, with about 40% one-month case fatality (2). About 50% of people suffering a sICH are using an antithrombotic (antiplatelet or anticoagulant) drug at symptom onset (3). The most common indication for antiplatelet drugs is secondary prevention of ischaemic events and for anticoagulant drugs it is stroke prevention in atrial fibrillation. People who suffer a sICH have an increased risk of ischaemic events, but also an increased risk of a new sICH (4-6). To date, there are no clear guidelines on whether people with sICH and an indication for an antithrombotic drug should (re)start them after sICH or not (7, 8). Both policies occur in clinical practice.

The STATICH protocol has been published (9). Some elements of the protocol are repeated below.

1.1 Aims of the study

The primary aim of Study of Antithrombotic Treatment after IntraCerebral Haemorrhage (STATICH) is to assess the effects of antithrombotic drugs on the risk of recurrent sICH.

The secondary aim is to assess whether brain imaging findings, such as cerebral microbleeds, modify the effects of antithrombotic drugs after sICH (9).

2 Study methods

2.1 Trial design

STATICH is a Scandinavian investigator-led, multicentre, randomised controlled open trial of antithrombotic drugs for prevention of ischaemic events in people with prior sICH. Originally, the study was designed as one trial, investigating the safety of antithrombotic drugs in people with prior sICH and an indication for antithrombotic drugs. From the time the study was planned and until the end of follow-up, the clinical question has changed. The scientific issue is now to investigate the safety and efficacy of antiplatelet drugs for people with an indication for antiplatelets, and the safety and efficacy of anticoagulants for people with atrial fibrillation and an indication for anticoagulants.

2.2 Ethical approvals

STATICH is conducted according to Good Clinical Practice and The Declaration of Helsinki. Regulatory agencies and research ethics committees in the three participating countries have approved the trial.

2.3 Randomisation

All participants eligible for inclusion were randomised using a central, web-based randomisation system. Participants with an indication of antiplatelet drugs were randomised in the antiplatelet part of the trial, whereas participants with atrial fibrillation and an indication for anticoagulant drugs were randomised in the anticoagulant part of the trial. For each of these trial parts, participants were randomised to either intervention (treatment with antithrombotic drugs) or open control using a minimisation algorithm without a pre-determined sequence. The first participant was randomly allocated with a probability of 0.5 to one of the arms. Adaptive minimisation was used to allocate each subsequent participant with a probability of 0.8 to the arm that minimises the difference between the arms, with respect to baseline characteristics (see below) in the previously randomised participants. The minimisation criteria are listed below.

2.3.1 Minimisation criteria in randomisation algorithm

- Age
 - o < 70 versus \geq 70 years
- Index sICH location
 - o Only supratentorial lobar regions are affected; yes versus no
- Probability of a good outcome at six months (10)
 - o < 0.15 versus \geq 0.15
- Days from index sICH to randomisation
 - o 0 to 6 days versus 7 to 30 days versus > 30 days
- Antiplatelet drug the patient's physician would use if allocated (this criterion only applies to the antiplatelet trial)
 - o Aspirin only; yes versus no

2.4 Sample size

The sample size estimation was made before the initiation of the study. A fourfold increase in the annual rate of recurrent sICH on antithrombotic drugs (from 2% to 8%) was considered unacceptable and higher than any plausible beneficial effect antithrombotic drugs would have on ischaemic events.

With power of 80% and a 5% significance level to detect an increase of the annual rate of recurrent sICH from 2% to 8% with antithrombotic therapy, the sample size was estimated to 500 participants randomised to intervention versus control. The sample size estimation was made for the trial as a whole, and not as two separate trials investigating the effect and safety of antiplatelets and effect and safety of anticoagulants as two separate trials. No sample size estimation for the two separate trials was performed. Regardless of this, analyses will be made for antiplatelet treatment versus control and anticoagulant treatment versus control separately.

2.5 Timing of outcome assessments

Outcomes will be assessed by study-personnel who are blinded to treatment allocation. Outcome assessment will take place by telephone interview with participants, participants relatives or health professionals every six months. Participants will be followed up for a minimum of two years. The inclusion period run longer than initially planned due to slow recruitment. The last participant was included December 2022 and per protocol the follow-up should continue until December 2024. Due to lack of resources the Trial Steering Committee decided in February 2024 to end follow-up in August 2024, leaving four participants not reaching two-year follow-up.

2.6 Timing of final analysis

Final analysis will take place after the follow-up period ends August 31st 2024. We will perform primary analysis on all patients who reached two-year follow-up. We will also

perform secondary analysis for total follow-up time for patients followed up for longer than two years.

3 Statistical principles

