3.4 Analysis populations

To preserve the benefit of randomisation, we will include all randomised participants in the analysis (irrespective of whether they adhere to the allocated treatment), all retained in the group to which they were allocated (i.e. "intention-to-treat" analysis). We will also consider conducting per-protocol analysis including randomised participants without major protocol deviations.

4 Trial population

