4.3 Withdrawal/loss-to-follow-up

Follow-up will be censored at death (unrelated to an outcome event), last available follow-up (if less than two years), or voluntary withdrawal from the trial.

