5.1 Outcome definitions

5.1.1. Primary outcome:

The primary outcome is new symptomatic sICH (fatal or non-fatal) found on CT scan, MRI scan or by autopsy over at least two years follow-up. We will perform analysis of time to first event after two years follow-up as primary analysis and after total follow-up time as

secondary analysis. Those not experiencing the event will be censored at last available follow-up, death unrelated to a primary outcome or voluntary withdrawal from the trial (whichever occurs soonest).

5.1.2. Secondary outcomes:

Secondary outcomes will be analysed as composite endpoints except for functional outcome at two years (according to modified Rankin Scale) and death of any cause. The secondary endpoints will also be reported individually. Secondary outcomes will be analysed as reported by investigator.

5.1.2.1 Composite secondary outcomes:

The following composite endpoints will be analysed:

- **Major ischaemic events:** Ischaemic stroke, myocardial infarction, mesenteric ischaemia, peripheral arterial occlusion, deep vein thrombosis, pulmonary embolism, revascularisation procedures (carotid, coronary or peripheral)
- **Major haemorrhagic events:** symptomatic intracerebral haemorrhage, other symptomatic intracranial haemorrhages (epidural, subdural or subarachnoid haemorrhages both spontaneous and traumatic), symptomatic major extracranial haemorrhage requiring transfusion with more than 2 units of whole blood or red cells, a fall in > 2.0 g/L haemoglobin, bleeding in a critical area or organ (intraspinal, intraocular, retroperitoneal, intra-articular or pericardial, or intramuscular with compartment syndrome) or haemorrhage leading to death.
- **Major adverse cardiovascular events (MACE)** defined as ischaemic stroke, myocardial infarction, other major ischaemic events, intracerebral haemorrhage, other intracranial haemorrhage, major extracranial haemorrhage or vascular death.

Time to event for secondary outcomes except for functional outcome according to modified Rankin Scale will be defined in the same way as for primary outcome. Modified Rankin Scale is not subject to survival analysis and thus time to event is irrelevant for this outcome.

As for the primary outcome, secondary outcomes will be analysed as time to first event after two-years follow-up and after total follow-up time.

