5.2.1 Primary analysis

Primary analysis is a comparison between groups of time-to-first event of new symptomatic sICH during two-year follow-up. This will be assessed by generating life tables, Kaplan-Meier curves and applying log-rank test.

The sample size calculation, performed before the study was started, is based on comparisons of proportions. However, in the protocol (latest protocol version v210421), time-to-event-analysis is defined as primary analysis. We will follow the protocol.

To adjust the differences between the groups, Cox proportional hazards (PH) regression model will be used. The results will be presented as an adjusted hazard ratio with the corresponding 95% CI.

All regression analyses will be adjusted for the variables being part of the minimisation criteria. If adjustment for all these variables is not possible due to few events (and consequently low power), age (< 70 versus \geq 70) and ICH location will be prioritized.

If the PH assumption is violated, time-dependent covariates will be included.

Since death is a competing risk, we will perform competing risk model as a sensitivity analysis.

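### Section 2.6 defines the primary analysis set by completed two-year follow-up, which conflicts with the intention-to-treat set and the censoring rules elsewhere in the SAP

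*SAP*

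**What the plan says.** Section 2.6 states: "We will perform primary analysis on all patients who reached two-year follow-up". It then says that the trial team will also "perform secondary analysis for total follow-up time for patients followed up for longer than two years". Just before this, section 2.5 explains that follow-up was stopped early, in August 2024, "leaving four participants not reaching two-year follow-up".

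Other sections define the same analysis differently:

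- Section 3.4, on populations: "we will include all randomised participants in the analysis (irrespective of whether they adhere to the allocated treatment", with each participant kept in the allocated group.
- Section 4.3, on censoring: "Follow-up will be censored at death (unrelated to an outcome event), last available follow-up (if less than two years", or voluntary withdrawal.
- Section 5.1.1, on the endpoint: "The primary outcome is new symptomatic sICH (fatal or non-fatal) found on CT scan, MRI scan or by autopsy". On those without an event: "Those not experiencing the event will be censored at last available follow-up, death unrelated to a primary outcome", or withdrawal.
- Section 5.2.1, on the method: "Primary analysis is a comparison between groups of time-to-first event of new symptomatic sICH during two-year follow-up". It adds a competing-risk model for death as a sensitivity analysis.

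**The concern.** Whether a participant reaches two years is known only after randomisation and depends on survival and retention, both of which treatment can affect. A primary set defined that way is not the intention-to-treat set. In a trial whose primary outcome is recurrent sICH, it also removes the most serious outcomes, because a participant who dies of a recurrence within two years has not reached two-year follow-up.

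The sentence can be read as a selection rule in two ways. Literally, it excludes everyone who died, withdrew or was lost before two years. Narrowly, taken with section 2.5, it excludes only the four participants affected by the early stop. Either way it departs from 3.4, 4.3 and 5.1.1. The SAP does not say which section takes precedence, so one analyst could follow 2.6 and another 3.4, and each would be following the plan. The second sentence of 2.6 has the same form and would limit the total follow-up analysis to people observed beyond two years.

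**Working it through.** **Comparison of the sections.** The SAP gives no figure for the size of this set, so the first check is of the text.

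| Participant | Section 2.6, literal | Sections 3.4, 4.3, 5.1.1 |
|---|---|---|
| Fatal recurrent sICH before two years | excluded | included as an event |
| Death from another cause before two years | excluded | included, censored at death |
| Withdrawal or loss before two years | excluded | included, censored |
| Four participants stopped in August 2024 | excluded | included; censored if event-free |

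If everyone in the set had reached two years, nobody could be censored earlier and there would be no deaths for the two-year competing-risk model. Those rules would have nothing to act on, so 2.6 taken literally is incompatible with them.

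**Size under the literal reading.**

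From the SAP: annual recurrence of 2% and 8% and a planned total of 500 (section 2.4). Assumed: 250 per arm, constant hazards, no withdrawals, other-cause mortality of 10% per year (range 5% to 15%), and 40% of recurrences fatal (range 20% to 50%). The SAP introduction gives about 40% one-month fatality for sICH in general, not for recurrences.

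Hazards: h0 = −ln 0.98 = 0.0202; h1 = −ln 0.92 = 0.0834, so the true hazard ratio is 4.13; m = −ln 0.90 = 0.1054. Fatality of recurrences is c.

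- Events by two years, all randomised: h/(h+m) × [1 − exp(−2(h+m))] = 3.57% and 13.89%. Times 250 per arm: 8.9 + 34.7 = 43.7 with rounding.
- Events kept among those alive at two years: (1−c) × [1 − exp(−2h)] × exp(−2m).
  - Control: 0.6 × 0.0396 × 0.81 = 1.92%, or 4.8 events.
  - Treatment: 0.6 × 0.1536 × 0.81 = 7.47%, or 18.7 events.
  - Total: 23.5, and 23.5/43.7 = 54% kept.
- Participants kept: event-free survivors, exp(−2(h+m)), plus the surviving events above. This gives 199.3 + 190.1 = 389.4 of 500, so about 111 are excluded.
- Over the assumed ranges: 76% of events are kept at 20% fatality and 5% mortality (34.9 of 46.0), and 42% at 50% fatality and 15% mortality (17.4 of 41.4).

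**Effect on the hazard ratio.** Conditioning on two-year survival cancels m, leaving an event rate in the restricted set of

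(1−c)(1 − e^(−2h)) / [2e^(−2h) + (1−c)((1 − e^(−2h))/h − 2e^(−2h))].

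| True HR | Fatality, control | Fatality, treatment | Apparent HR |
|---|---|---|---|
| 2.0 | 40% | 40% | 2.02 |
| 4.13 | 40% | 40% | 4.23 |
| 2.0 | 40% | 60% | 1.36 |
| 2.0 | 60% | 40% | 3.01 |

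The unequal-fatality rows are illustrations; the SAP gives no figure for fatality by arm.

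**Size under the narrow reading.** Inclusion ended in December 2022, so each of the four has at least 1.67 years of potential follow-up by 31 August 2024. Lost person-time is 4 × 1.67 = 6.7, up to 4 × 2 = 8 person-years. Expected events are 4 × [1 − exp(−h t)]: 0.13 at 2% per year over 1.67 years, and 0.61 at 8% per year over 2 years. Four of 500 is 0.8%.

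**The case against.** The strongest defence is context. Section 2.6 is about timing and follows directly on the account of the early stop, reusing its phrase about reaching two years. The population is set in 3.4, and 4.3, 5.1.1 and 5.2.1 all fit a two-year horizon on everyone randomised. An analyst would have to override all of these to run a survivors-only analysis. The second sentence may mean only that people followed beyond two years are the ones who add time. On size, mortality and fatality are assumed, the 8% rate is the increase that section 2.4 calls unacceptable rather than an expected rate, and the 500 pools two trial parts that section 5.2 analyses separately.

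Much of this stands. The likely intent is benign, the literal reading is the less probable of the two, and the event counts are illustrative rather than a forecast for either trial part. It does not remove the problem. The sentence names patients, not a time window, and no section says that it sets only the horizon. Even the administrative reading drops four participants whom section 4.3 keeps and censors.

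**Conclusion.** The concern holds. As worded, 2.6 conflicts with the SAP's own intention-to-treat and censoring rules, and that finding rests on the text alone. It should be fixed before analysis, though nothing suggests that a survivors-only analysis is intended.

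The consequence depends on the reading. The literal one would discard 24% to 58% of expected two-year primary events under the assumptions shown. It would leave the hazard ratio almost unchanged if recurrences are equally fatal in both arms, and could understate or overstate harm substantially if they are not. The narrow one loses less than one expected event, but departs from intention-to-treat for no gain, since censoring already deals with those participants.

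**What to change.** Replace the two sentences in section 2.6 with wording such as:

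> The primary analysis covers every participant randomised in the trial part concerned, analysed in the allocated arm. Time from randomisation to first symptomatic sICH is truncated at two years. Fatal sICH is an event. Event-free participants with shorter follow-up, including any of the four affected by the August 2024 stop, are censored under 4.3 and 5.1.1.
>
> The secondary analysis covers the same participants over total follow-up, under the same event and censoring rules, without truncation at two years.

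Apply the same set to the time-to-event secondary outcomes. The cost is two passages of wording in one section. No new data are needed, and 3.4, 4.3, 5.1.1 and 5.2.1 stay as they are.

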3.1 General considerations

This analysis plan will apply for the primary aim of the STATICH study.

3.2 Confidence intervals and p-values

The results with p-values below 0.05 will be considered statistically significant, unless otherwise specified. The differences between the groups will be presented with 95% confidence intervals (CIs). All statistical tests will be two-sided.

3.3 Adherence and protocol deviations

3.3.1 Adherence to allocated treatment

Adherence to the intervention will be assessed by open follow-up from unblinded study-personnel every six months during the follow-up period. Adherence will be described for each treatment group, but no statistical tests will be performed.

3.3.2 Protocol deviations

Important protocol deviations are deviations that may significantly impact the completeness, accuracy, and reliability of the study data or that may significantly affect a participant's rights, safety or well-being. The following are considered important protocol deviations in this study:

- Participants randomised despite not meeting the entry criteria.
- Participants who received the wrong treatment or incorrect dose.
- Participants who received an excluded concomitant treatment.
- Absence of source documents.
- Failure to collect data on the primary or secondary endpoints.

We will list all important protocol deviations, but no formal statistical testing will be performed.

3.4 Analysis populations

To preserve the benefit of randomisation, we will include all randomised participants in the analysis (irrespective of whether they adhere to the allocated treatment), all retained in the group to which they were allocated (i.e. "intention-to-treat" analysis). We will also consider conducting per-protocol analysis including randomised participants without major protocol deviations.

4 Trial population

4.1 Eligibility criteria

4.1.1 Inclusion criteria

[figure not shown]
1. People aged ≥ 18 years of age
2. Non-traumatic, sICH at least 24 hours ago without a preceding traumatic brain injury, based on history from the patient/witness of spontaneous symptom onset and brain imaging appearance consistent of sICH.
3. No underlying structural cause (e.g. aneurysm, tumour, arteriovenous malformation, intracerebral venous thrombosis, or haemorrhagic transformation of an ischaemic stroke)
4. Indication for antithrombotic (i.e. anticoagulant or antiplatelet) drug for the prevention of ischaemic events, either antiplatelet drugs for patients with vascular disease, or anticoagulant drug for patients with atrial fibrillation
 - a. Indication for antiplatelet drugs can be previous ischaemic stroke, myocardial infarction, other occlusive arterial disease, or arterial stents or other arterial implants (secondary prevention), or patients with known significant atherosclerotic arterial disease, such as carotid or coronary artery stenosis or mobile aortic atheroma (primary prevention)
5. Consent to randomisation from the patient (or personal/legal/professional representative, if the patient does not have mental capacity to give consent, and waiver of consent is acceptable in the patient's country)
6. CT and/or MRI is performed before randomisation

4.1.2. Exclusion criteria:

1. Clear indication for antiplatelet or anticoagulant treatment (e.g. recent coronary artery stenting, or prosthetic metallic heart valves)
2. Contraindications to the antithrombotic drug that will be administered
3. Patient is pregnant, breastfeeding or of childbearing potential and not using contraception
 - a. A woman of childbearing potential must undergo a pregnancy test before randomisation and the result must be recorded in the case report form.
 - b. Women of childbearing potential randomised to active treatment must use effective methods of contraception and undergo regular pregnancy testing during follow-up, and the results must be recorded in the case report forms.
4. Malignancy with life expectancy less than two years
5. For MRI examination: Contraindication to the brain MRI

4.2 Recruitment

Participants may be recruited during their hospital admission for the qualifying sICH or at a later stage in an outpatient clinic.

Trial flow chart

4.3 Withdrawal/loss-to-follow-up

Follow-up will be censored at death (unrelated to an outcome event), last available follow-up (if less than two years), or voluntary withdrawal from the trial.

4.4 Baseline patient characteristics

4.4.1 Baselines variables

The following baseline variables will be reported: Age, sex, comorbidities, living arrangements, functional status at randomisation, medications used before randomisation, physiological parameters, time from sICH to randomisation, location (non-lobar versus lobar) and volume (< 30 ml versus \geq 30 ml) of sICH on CT or MRI before randomisation.

4.4.2 Descriptive statistics of baseline characteristics

Continuous variables will be presented using means and standard deviations (SDs), medians and minimum and maximum value, and quartiles. Categorical data will be presented using frequencies and percentages.

5 Analysis

5.1 Outcome definitions

5.1.1. Primary outcome:

The primary outcome is new symptomatic sICH (fatal or non-fatal) found on CT scan, MRI scan or by autopsy over at least two years follow-up. We will perform analysis of time to first event after two years follow-up as primary analysis and after total follow-up time as

secondary analysis. Those not experiencing the event will be censored at last available follow-up, death unrelated to a primary outcome or voluntary withdrawal from the trial (whichever occurs soonest).

5.1.2. Secondary outcomes:

Secondary outcomes will be analysed as composite endpoints except for functional outcome at two years (according to modified Rankin Scale) and death of any cause. The secondary endpoints will also be reported individually. Secondary outcomes will be analysed as reported by investigator.

5.1.2.1 Composite secondary outcomes:

The following composite endpoints will be analysed:

- **Major ischaemic events:** Ischaemic stroke, myocardial infarction, mesenteric ischaemia, peripheral arterial occlusion, deep vein thrombosis, pulmonary embolism, revascularisation procedures (carotid, coronary or peripheral)
- **Major haemorrhagic events:** symptomatic intracerebral haemorrhage, other symptomatic intracranial haemorrhages (epidural, subdural or subarachnoid haemorrhages both spontaneous and traumatic), symptomatic major extracranial haemorrhage requiring transfusion with more than 2 units of whole blood or red cells, a fall in > 2.0 g/L haemoglobin, bleeding in a critical area or organ (intraspinal, intraocular, retroperitoneal, intra-articular or pericardial, or intramuscular with compartment syndrome) or haemorrhage leading to death.
- **Major adverse cardiovascular events (MACE)** defined as ischaemic stroke, myocardial infarction, other major ischaemic events, intracerebral haemorrhage, other intracranial haemorrhage, major extracranial haemorrhage or vascular death.

Time to event for secondary outcomes except for functional outcome according to modified Rankin Scale will be defined in the same way as for primary outcome. Modified Rankin Scale is not subject to survival analysis and thus time to event is irrelevant for this outcome.

As for the primary outcome, secondary outcomes will be analysed as time to first event after two-years follow-up and after total follow-up time.

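### Major ischaemic events and MACE count any revascularisation, so in this open trial a procedure chosen with the allocation known can be the scored first event, and no analysis without procedures is planned

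*SAP*

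**What the plan says.** In SAP section 5.1.2.1 the list for Major ischaemic events ends with "revascularisation procedures (carotid, coronary or peripheral"). Nothing in the SAP limits this to urgent or unplanned procedures, to procedures after a new event, or to disease found after randomisation. MACE is "defined as ischaemic stroke, myocardial infarction, other major ischaemic events, intracerebral haemorrhage, other intracranial haemorrhage, major extracranial haemorrhage or vascular death", so revascularisation enters it as one of the other major ischaemic events. Section 5.1.2 analyses both composites as time to first event, at two years and over total follow-up, and says that the secondary endpoints will also be reported one by one.

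Four other places bear on the point:

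- Section 4.1.1, criterion 4a, lists the indications for antiplatelet drugs. After the secondary-prevention indications it adds "patients with known significant atherosclerotic arterial disease, such as carotid or coronary artery stenosis or mobile aortic atheroma (primary prevention").
- Section 2.1 describes a "multicentre, randomised controlled open trial of antithrombotic drugs", and section 2.3 says that participants were "randomised to either intervention (treatment with antithrombotic drugs) or open control".
- Section 2.5 states: "Outcomes will be assessed by study-personnel who are blinded to treatment allocation".
- Section 5.1.2 states: "Secondary outcomes will be analysed as reported by investigator".

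**The concern.** Most components of the ischaemic composite are things that happen to a patient. Revascularisation is something that clinicians decide to do. Here they know the allocation, and the SAP itself links procedures with antithrombotic treatment: exclusion criterion 1 gives recent coronary stenting as an example of a clear indication for these drugs. It is plausible that a clinician weighing a stent would decide differently for a participant allocated to avoid antiplatelet drugs than for one already taking them. The frequency of procedures could then differ between arms without any difference in ischaemia.

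Some antiplatelet participants may also have entered with a known stenosis that could be treated electively during follow-up. Under the definition, that procedure scores the same as an ischaemic stroke. If it comes first, a later stroke or infarction no longer contributes to the composite.

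Section 2.1 says the question has become one of safety and efficacy. Major ischaemic events is the composite that speaks most directly to efficacy, and MACE is the one that weighs benefit against harm. Both would be affected.

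**Working it through.** **1. Does any text restrict the component or remove the problem?**

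| Possible safeguard | What the SAP provides | Does it suffice? |
|---|---|---|
| Qualifier in the definition | None in 5.1.2.1 | No |
| Exclusion criterion 1 | Names recent coronary stenting | Partly: it does not name planned procedures or untreated stenosis |
| Blinded assessment (2.5) | Blinds those who assess outcomes | No: the procedure really happened, and the decision was made unblinded |
| Adjudication | Secondary outcomes taken as the investigator reports them (5.1.2) | No filtering step is stated |
| Individual reporting (5.1.2) | Each component shown | Partly: separate results do not combine into a time-to-first-event hazard ratio for the composite without procedures |

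**2. Size.** The SAP gives no event rate, effect size or power for either composite, so there is no figure to reproduce. Everything below rests on assumed values.

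*Two-year risks.* Assume the other ischaemic components occur in 10% of controls and 7% of treated participants (7/10 = 0.70), and that nobody has both a procedure and another component. With procedures in r_t % of treated and r_c % of controls, the risk ratio is (7 + r_t)/(10 + r_c).

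| r_t | r_c | Risk ratio |
|---|---|---|
| 1 | 1 | 8/11 = 0.727 |
| 2 | 2 | 9/12 = 0.750 |
| 4 | 4 | 11/14 = 0.786 |
| 4 | 2 | 11/12 = 0.917 |
| 2 | 4 | 9/14 = 0.643 |

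*Hazards.* Let s be the share of control-arm first events that are procedures, and k the treated-to-control ratio of procedure rates. With a true hazard ratio of 0.70 for the rest, the composite is about (1 − s) × 0.70 + s × k.

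| s | k = 1 | k = 1.25 | k = 0.8 |
|---|---|---|---|
| 0.10 | 0.63 + 0.10 = 0.73 | 0.63 + 0.125 = 0.755 | 0.63 + 0.08 = 0.71 |
| 0.40 | 0.42 + 0.40 = 0.82 | 0.42 + 0.50 = 0.92 | 0.42 + 0.32 = 0.74 |

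The composite always lies between 0.70 and k. It overstates benefit only if open allocation makes procedures rarer under treatment by more than the drug's own effect (k below 0.70, as in the last row of the first table).

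*Power.* Schoenfeld's formula for 80% power at two-sided 5%, d = 4(1.960 + 0.842)²/(ln HR)², gives 247 events at 0.70, 317 at 0.73 and 798 at 0.82. Adding procedures also adds events, so the comparison must allow for that. If events are proportional to hazards, 247 events without procedures become 247 × (1 + 0.73)/(0.90 + 0.63) = 279 at s = 0.10, against 317 needed. At s = 0.40 they become 247 × (1 + 0.82)/(0.60 + 0.42) = 441, against 798 needed. Under these assumptions the extra events do not make up for the dilution.

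The hazard illustration is for Major ischaemic events. MACE also contains haemorrhages and vascular death, so procedures would make up a different share of it.

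**The case against.** Counting revascularisation in an ischaemic composite is a legitimate design choice, and some procedures do reflect progressing disease. Nothing in the SAP contradicts the definition, and the protocol, which is not shown, may narrow it. These points stand, and they are reasons to leave the composites as they are.

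A reader might infer that planned treatment of the entry disease is in fact being scored as an ischaemic event. The document does not support that. It nowhere says that anyone was randomised with a procedure planned, and exclusion criterion 1 may have kept some such people out. Stenosis is an example within one of several entry routes, and it concerns the antiplatelet part only. The anticoagulant part enrols on atrial fibrillation and is analysed separately (section 5.2), so only the open-allocation argument reaches it.

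The illustrations are also open to challenge. Adding risks assumes no overlap, although procedures may often accompany a stroke or infarction that already counts, so the shift is probably overstated. The ratios 0.917 and 0.643 need a twofold difference in procedures between arms, for which the SAP offers no evidence. Precision will be poor in any case. If the planned 500 split evenly into 125 per arm in each part (an assumption), risks of 10% and 7% mean 12.5 and 8.75 events. The standard error of the log risk ratio is √(1/8.75 − 1/125 + 1/12.5 − 1/125) = 0.42, and the 95% interval about 0.70 runs from about 0.31 to 1.60. Symmetric dilution is small beside that.

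This limits the weight of the point but does not remove it. Wide intervals do not correct a bias, and individual reporting does not supply the composite without procedures.

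**Conclusion.** The point holds in a limited form. As defined, both composites can take a clinician-decided procedure as the first event in an open trial, and no planned analysis shows how far the result depends on that. The likely consequence is dilution. A bias in either direction is possible, and the SAP does not allow its sign or size to be determined. The shifts to 0.73–0.82 (unaffected procedures) and to 0.64–0.92 (unequal procedures) rest wholly on assumed rates.

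A reader might conclude that the trial's main result is at risk or that the composites must be redefined. Neither follows. The primary outcome is recurrent symptomatic sICH and the sample size rests on it; revascularisation plays no part in either. Restricting the component to procedures after a new acute event would make it nearly redundant, since stroke, infarction and arterial occlusion already count. It would also need information on which procedures were planned, which the SAP does not show was collected, and it would change an endpoint late in an open trial. This is a cheap and worthwhile improvement to two secondary composites.

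**What to change.** Leave the definitions in 5.1.2.1 unchanged. Add to 5.2.2, before analysis begins, a sensitivity analysis of Major ischaemic events and of MACE with revascularisation left out. Use the same Kaplan-Meier, log-rank and Cox methods and the same covariates, in each trial part, at two years and over total follow-up. State that a participant who has a procedure stays at risk and is not censored at it, so that a later stroke or infarction counts on its own date. Report each result beside that of the full composite.

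Cost: 2 composites × 2 trial parts × 2 follow-up periods = up to 8 additional Cox models. The sensitivity analysis will have fewer events and hence wider intervals, and the rule in 5.2.1 for reducing covariates when events are few may apply more often. No new data are needed, because the components are already to be reported individually. The analysis does not undo any effect that a procedure itself has on later events, and the report should say so.
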